### **Analysis for the Tertiary Aims:**

**The effect of treatment on adherence status at 3-months.** Adherence will be measured as a continuous variable. A linear regression will be performed using the final assessment of adherence as a response and randomization group as a predictor. Other variables that may potentially have an effect on adherence such as age, gender, level of education and comorbidity will also be included if these variables are not balanced between groups by the randomization or if they are determined by univariate analysis to be significantly predictive of adherence.

**The effect of treatment on BP reduction at 3-months.** BP will be treated as continuous systolic BP (SBP) and diastolic BP (DBP) variables measured at baseline and 3-months. The effect of treatment on these variables over time will be assessed using differences in differences estimation whereby pre-intervention SBP and DBP values are subtracted from post-intervention values, and change amounts by study group are compared using t tests. The significance level will be set at  $\alpha=.05$ . Analysis of covariance will be used in place of a t test, if covariates are needed.

**The effect of treatment on HbA1c reduction at 3-months.** HbA1c will be treated as a continuous variable at baseline and 3 months. The effect of treatment on HbA1c over time will be assessed using differences in differences estimation whereby pre-intervention HbA1c values are subtracted from post-intervention values, and change amounts by study group are compared using t tests. The significance level will be set at  $\alpha=.05$ . Analysis of covariance will be used in place of a t test, if covariates are needed.

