**Data Management:** [name] will oversee the data management for this study. All data will be double entered by RAs and compared using automated comparison programs. Inconsistent data entry will be resolved against the raw data, and comparisons will continue until all inconsistency is removed. Periodically, [name] will review all data for duplicate records, illogical collection dates and contingencies, and outlier values using program syntax created for each file. Reasons for dropout and loss to follow-up will be tabulated by condition. The results of analyses using imputed values will be compared with the results obtained with only complete cases. If the results indicate that attrition is significantly related to one or more baseline variable, predicted values from a logit model will be used as a covariate in all subsequent analyses, thereby correcting for differential attrition. All randomized participants will be included using intent-to-treat analytic strategies. While randomization is expected to produce well-balanced groups, analyses will determine baseline differences between the groups on demographic or prognostic variables. If significant differences are found, these variables will be included in a logit model to predict group assignment, and predicted values from the final logit model will be used as a covariate in all subsequent analyses.

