Statistical Analytic Plan
Tailored Approaches to Improve Medication Adherence
NCT01643473
05/10/2018

Analysis of the qualitative data: [name] and a trained research assistant conducted the qualitative analysis of the audiotaped interview data. Transcripts of the interviews were uploaded to the Atlas.ti program in order to code the data and facilitate content analysis. The transcripts were individually reviewed and analyzed using the grounded theory constant comparison method. Specifically, transcripts were coded line-by-line using open coding (comparing and categorizing data to generate concepts); axial coding (reorganizing data into categories based on relationships within and between these categories); and selective coding (identifying and describing the central themes to generate a conceptual framework) according to issues related to medication-taking (e.g., side effects, cost, forgetfulness). Once the transcripts were independently coded, the research team met to discuss the coding and resolve any discrepancies.

Analysis of study feasibility: We assessed reach of the intervention by examining the ratio of eligible participants invited to participate vs. those that enroll in the study. We also collected data on patients' age and gender to determine if there are any differences between eligible participants that do not enroll vs. enrollees. Independent t-tests and the chi-square statistic were used to determine if there are any significant differences between the groups. Reasons for not enrolling in the program were also documented. In addition to these outcomes, exit interviews were conducted with a subsample of 12 participants to assess acceptability and satisfaction with the program.

Analysis of exploratory outcomes: To test the exploratory aim, we conducted separate differences in differences estimations for each of the outcome measures (i.e., adherence, BP HbA1c) whereby pre-intervention values are subtracted from post-intervention values, and change amounts by study group are compared using t tests. We also conducted linear regression models to examine whether the average baseline scores were significantly different from the average scores at 3 months, when, controlling for baseline levels of the outcome measure (i.e., adherence, BP HbA1c), age, gender socioeconomic status (SES), insurance status and number of medications

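### No clearly stated arm comparison of SBP, DBP or HbA1c always adjusts for the outcome's own baseline; the main test is a t test on change, which is valid but less precise

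*Protocol*

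**What the plan says.** **Protocol, section 10, Analysis for the Tertiary Aims.** For SBP and DBP, "pre-intervention SBP and DBP values are subtracted from post-intervention values, and change amounts by study group are compared using t tests". For HbA1c, "pre-intervention HbA1c values are subtracted from post-intervention values, and change amounts by study group are compared using t tests". Alpha is .05 for both. Each paragraph then adds: "Analysis of covariance will be used in place of a t test, if covariates are needed". It does not say when covariates count as needed, or which ones they would be.

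**Protocol, section 10, Data Management paragraph.** Baseline differences between the groups on demographic or prognostic variables are to be examined. "If significant differences are found, these variables will be included in a logit model to predict group assignment", and the predicted values from that model become a covariate in later analyses.

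**SAP, analysis of exploratory outcomes.** For adherence, BP and HbA1c alike, "pre-intervention values are subtracted from post-intervention values, and change amounts by study group are compared using t tests". A second analysis follows: "We also conducted linear regression models to examine whether the average baseline scores were significantly different from the average scores at 3 months", "controlling for baseline levels of the outcome measure (i.e., adherence, BP HbA1c), age, gender socioeconomic status (SES), insurance status and number of medications". Study group is not mentioned in that second model.

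**The concern.** A t test on change fixes the slope of the 3-month value on the baseline value at 1. For a measurement that varies between visits the slope is normally below 1, and more plainly so when patients are selected because that measurement was high. Two things follow. Precision is lost. And if one arm happens to start higher, that arm tends to show a larger fall without any treatment effect.

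With 15 to 20 patients per arm, chance differences at baseline are not small and there is little precision to spare. Section 2 states between-arm hypotheses for BP and HbA1c, and section 10 says the pilot will inform the power calculation for a larger trial. An effect estimate that carries avoidable noise, or is moved by a baseline imbalance, would pass into that design.

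**Working it through.** **Inputs from the documents.** 20 per group; 15% attrition; about 15 completers per group; alpha .05 (sidedness not given, taken as two-sided). No SD, effect size, correlation or power figure is stated for BP or HbA1c.

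**Assumptions.** Correlation r between baseline and 3 months of 0.3 to 0.7; equal SDs at the two visits before any truncation. Results are in SD units unless stated.

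**The plan's own figure.** 20 × 0.85 = 17 completers per group, not 15; 15 of 20 would be 25% attrition. I use 15, as stated. At 17 per arm the first ratios below become 0.67 to 0.88, so nothing here turns on it.

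**Step 1. Is baseline adjustment supplied anywhere?**
- The ANCOVA clause is conditional and does not name the baseline value.
- The imbalance rule acts only on a significant difference. At 15 per arm that requires 2.048 × √(2/15) = 0.75 SD. Below that nothing is done; above it, a group-assignment score is added, not necessarily the baseline value itself.
- The SAP regression includes baseline, but its stated question compares baseline means with 3-month means, and no group coefficient is named. It also carries five further covariates.

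**Step 2. Precision, baseline not truncated.**
- Variance of change: 2(1−r). ANCOVA residual variance: 1−r². Ratio: (1+r)/2.
- Cost of estimating the slope with 30 patients: 1 + 1/26 = 1.038.

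| r | (1+r)/2 | with slope cost | power for an assumed 0.5 SD effect, t test on change → ANCOVA |
|---|---|---|---|
| 0.3 | 0.65 | 0.68 | 20% → 27% |
| 0.5 | 0.75 | 0.78 | 26% → 32% |
| 0.7 | 0.85 | 0.88 | 40% → 44% |

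In patients: 30/0.68 = 44 and 30/0.88 = 34, so the gain is worth about 14 to 4 patients on 30. Simulation of 40,000 trials per value of r gave variance ratios of 0.68, 0.78 and 0.88.

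**Step 3. Precision, baseline truncated by the entry threshold.** Let v₀ be the baseline variance after truncation: 0.36 if cut at the mean, 0.49 if cut 0.5 SD below it. The ratio is (1−r²) / [(1−r²) + (1−r)²v₀].
- Largest gain (r = 0.3, v₀ = 0.49): 0.91/(0.91 + 0.49 × 0.49) = 0.79; × 1.038 = 0.82.
- Smallest gain (r = 0.7, v₀ = 0.36): 0.51/(0.51 + 0.09 × 0.36) = 0.94; × 1.038 = 0.98.

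Simulation at 15 per arm gave 0.82 to 0.97. In patients: 30/0.82 = 37 and 30/0.98 = 31, so about 7 to 1 on 30.

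**Step 4. Effect of a chance baseline difference.** Given an observed difference D (intervention minus education), the change-score effect shifts by −(1−slope) × D. The SE of D is √(2/15) = 0.37 SD. For D of that size the shift is 0.26, 0.18 or 0.11 SD at slope 0.3, 0.5 or 0.7. Simulation reproduced these values, with about zero for ANCOVA. At slope 0.5, a D just under the 0.75 SD trigger leaves 0.5 × 0.75 = 0.37 SD uncorrected.

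In mmHg, with an assumed baseline SD of 10 to 15, the SE of D is 3.7 to 5.5, and half of it (1.8 to 2.7) enters the effect at slope 0.5. If 10 to 15 is the SD before truncation, the truncated SD is 0.60 to 0.70 of it and the shift is about 1.1 to 1.9.

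**Step 5. Can the SAP's larger model stand in?** For covariates that predict nothing, the variance factor with k covariates and 30 patients is 27/(27−k). Going from k = 1 to k = 6 gives (27/21)/(27/26) = 1.24, a 24% increase. This is a worst case; predictive covariates would offset it.

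**The case against.** The strongest reply is that baseline adjustment is already in the SAP. Its regression sits under the exploratory aim and controls for the baseline level of the outcome. A pure before-after comparison would hardly control for baseline, so a baseline-adjusted arm comparison may well have been intended. That is plausible, and it means a reader who infers that the plan contains no baseline adjustment goes too far. The protocol's ANCOVA clause does not exclude baseline either, and baseline BP or HbA1c could count as prognostic variables under the imbalance rule. But none of these texts names a group effect adjusted for the outcome's own baseline in every case.

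A reader might also infer that the change-score test is biased or invalid. It is not: over randomisations it is unbiased, and the simulated means were about zero. The shift in Step 4 is conditional on the imbalance observed. The test also matches the stated endpoint of reduction from baseline.

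A third temptation is to take (1+r)/2 at face value, which gives 16 to 5 patients on 30. That leaves out the cost of estimating the slope and assumes untruncated baselines. Whether baselines are truncated is itself unclear. Section 9 joins the BP and A1c entry conditions with *and*, while sections 2 and 4 join hypertension and diabetes with *or*; within BP, either SBP or DBP suffices. These passages must be reconciled, and both ranges are therefore shown.

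Finally, the SAP is written in the past tense, so replacing the main test may now be a post hoc change. That stands and shapes the fix.

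**Conclusion.** The point holds as one of precision and clarity. Both documents make the t test on change the main arm comparison for SBP, DBP and HbA1c, and no clearly stated alternative always adjusts for the same measure's baseline. Under the assumptions above, adjustment would cut the variance by about 12 to 32% with untruncated baselines and about 2 to 18% with truncated ones. The gain shrinks as r rises; at r = 0.8 without truncation it is about 7%. The correlation, SDs and slope are assumed throughout.

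These are tertiary outcomes, called exploratory in the SAP, in a 40-patient pilot that declines to state power. No stated figure or confirmatory conclusion is overturned. The change is worth making because the baseline values are already collected at the first visit.

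**What to change.** - In the protocol's Analysis for the Tertiary Aims and in the SAP's exploratory-outcomes paragraph, make the main analysis of SBP, DBP and HbA1c a regression of the 3-month value on randomised group plus the baseline value of the same measure, unconditionally. Report the group coefficient with its 95% CI.
- In the SAP regression, name the study-group term and reword its question as a comparison between arms.
- Keep the t test on change and the model with the five further covariates as sensitivity analyses.
- If the analyses are already complete, report the adjusted comparison beside the t test and label it a re-analysis.

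The cost is one degree of freedom and a change of wording, or one short re-analysis. No new data are needed.

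### Covariate adjustment is triggered by baseline significance tests and governed by several unranked rules; one pre-specified baseline-adjusted ANCOVA per outcome would be clearer and more powerful

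*Protocol*

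**What the plan says.** The documents hold several covariate rules for the same three outcomes (adherence, BP, HbA1c).

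- **Protocol section 10, Data Management paragraph.** "While randomization is expected to produce well-balanced groups, analyses will determine baseline differences between the groups on demographic or prognostic variables". Any variable that differs significantly then goes into a logistic model for arm, after which "predicted values from the final logit model will be used as a covariate in all subsequent analyses". The same paragraph has a second conditional score, for dropout, which likewise enters every later model: "If the results indicate that attrition is significantly related to one or more baseline variable, predicted values from a logit model will be used".
- **Protocol section 10, Analysis for the Tertiary Aims, adherence.** The final score is regressed on group; baseline adherence is not named as a covariate. Age, gender, education and comorbidity are given as examples of variables that "will also be included if these variables are not balanced between groups by the randomization", or if a univariate analysis finds them predictive. No threshold for imbalance is given.
- **Same section, BP and HbA1c.** Change scores are compared by t test. "Analysis of covariance will be used in place of a t test, if covariates are needed"; what makes a covariate needed is not defined.
- **SAP, Analysis of exploratory outcomes.** Change-score t tests for all three outcomes, plus linear regressions adjusting for the baseline outcome and "age, gender socioeconomic status (SES), insurance status and number of medications". The regression is described as comparing baseline with 3-month averages, and no group term is named. The logit score is neither mentioned nor withdrawn.

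No text says which rule governs or which result is the main one.

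**The concern.** In a properly randomised trial a significant baseline difference is a chance event. A test for it shows which variables happened to differ, not which ones predict the outcome. A score fitted to predict group is correlated with group by construction. If its variables are not prognostic, it takes information from the treatment comparison and gives nothing back. The obvious prognostic covariate, the baseline value of the outcome, is already measured for all three outcomes (Measures table, section 9).

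At stake are precision and a defined estimator. The pilot is meant to inform the power of a larger trial. An estimate and standard error that depend on which imbalances arose, and on which of several rules was followed, are poor inputs for that.

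**Working it through.** **1. The plan's own figures.** No effect size, SD or power is given; the sample-size paragraph says the data are insufficient. For completers, 20 × (1 − 0.15) = 17 per arm, whereas the protocol says about 15 (which would be 25% loss, 1 − 15/20). That mismatch is a separate matter. The check uses 17 per arm, with 15 and 20 as bounds.

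**2. How often the trigger fires.** For k independent tests at an assumed 0.05 (no level is stated for baseline tests), P(at least one significant) = 1 − 0.95^k:

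- k = 5: 0.226
- k = 10: 0.401
- k = 20: 0.642

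The probability passes one half between k = 13 (0.487) and k = 14 (0.512). The Measures table has 20 first-visit rows, but one is the chart review, some are probably correlated, and a row may hold several variables. So k is unknown in both directions.

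**3. Collinearity.** For one covariate just reaching p = 0.05 with 34 completers (32 df, t = 2.037), r² = t²/(t² + df) = 4.149/36.149 = 0.115. The variance inflation factor is 1/(1 − 0.115) = 1.13, or √1.13 = 1.06 on the SE. This is the collinearity part only. The net SE also depends on how much residual variance the covariate removes.

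**4. Simulation.** Assumptions not in the documents: effect 0.8 SD; baseline-to-3-month correlation 0.3, 0.5 or 0.7; 11 tested variables (the outcome plus 10 independent ones, 3 of them weakly prognostic); two-sided 0.05; 3,000 trials per setting. The logit rule means baseline tests, then the score added to the change-score model if triggered. Power (%) at 17 per arm:

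| Correlation | Change t test | Logit rule | Baseline ANCOVA | Cost of score | ANCOVA over logit rule |
|---|---|---|---|---|---|
| 0.3 | 47.3 | 43.6 | 64.9 | 3.7 | 21.3 |
| 0.5 | 61.9 | 58.4 | 73.5 | 3.5 | 15.1 |
| 0.7 | 83.6 | 80.9 | 88.3 | 2.7 | 7.4 |

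- With 20 tested variables, power for t test, logit rule and ANCOVA is 61, 54 and 73 at correlation 0.5, and 83, 77 and 88 at 0.7: a cost of 7 and 6 points. With 5 variables the cost is about 1 point.
- Across all such runs at 17 per arm, ANCOVA has 64 to 88% against 42 to 83% for the logit rule: gains from 88 − 83 = 5 to 64 − 42 = 22 points.
- At correlations 0.3, 0.5 and 0.7, ANCOVA against the logit rule is 60 v 41, 67 v 50 and 82 v 74 at 15 per arm, and 73 v 53, 80 v 69 and 92 v 87 at 20 per arm.
- When triggered, the score raises the SE by about 8 to 11% at 17 to 20 per arm, and by 12 to 13% at 15.
- When only the baseline outcome triggers, the SE ratio is about 0.90 to 0.99 at correlation 0.3 to 0.5, and about 1.02 at 0.7.

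**5. Where the gain comes from.** The variance of the group contrast is proportional to 2(1 − ρ) for a change score and 1 − ρ² for ANCOVA, a ratio of (1 + ρ)/2 = 0.65, 0.75 and 0.85 at ρ = 0.3, 0.5 and 0.7. In the table, replacing the change score accounts for 64.9 − 47.3 = 17.6 of 21.3 points, 11.6 of 15.1, and 4.7 of 7.4. With 20 variables it is 12 of 19 at correlation 0.5 but 5 of 11 at 0.7, so there the score matters about as much.

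**6. Type I error.** The logit rule alone gives 3.5 to 4.3%. If whichever of four analyses was favourable could be reported (logit rule, the protocol's adherence rule, SAP t test, SAP regression with a group term supplied), it would be 10 to 12%. At effect 0.8 the four disagree on significance in 36 to 50% of trials.

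**The case against.** The strongest reply is that the SAP already settles the matter. It mentions no baseline testing and no score, its covariate list is fixed and includes the baseline outcome, and it addresses an aim that the protocol frames as a between-group comparison. The regression may simply be a loosely worded ANCOVA. With a group term supplied, it has 63 to 91% power in the simulation at 17 per arm, close to baseline ANCOVA. This reading is plausible, but it rests on silence: the SAP does not withdraw the protocol rule, name the group term or rank the regression against its t tests.

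For BP and HbA1c, the provision for ANCOVA can also be read as carried out through the logit score, so the rules need not conflict there. The clear clash is for adherence, where one rule adds raw variables and another adds a score.

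A reader might also infer more than the documents support:

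- *That the rule usually fires.* This needs about 14 or more independent tests, and the protocol gives no count.
- *That the score always inflates the standard error.* As a net statement this is false. If the baseline outcome is the trigger, the score can lower it.
- *That the score explains the whole power gap to ANCOVA.* Most of the gap usually comes from the change score.
- *That false positives are inflated.* The rule alone does not do this. The 10 to 12% assumes free choice among analyses, which the documents leave open but do not state.

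**Conclusion.** The point holds in a limited form. The plan has a significance-triggered group-assignment score, other data-driven triggers for the same outcomes, and a SAP that neither withdraws nor ranks them. The trigger does not select for prognosis. At 17 per arm the score costs about 1 to 7 power points against the change-score t test, and a pre-specified baseline ANCOVA gains about 5 to 22 points over the logit rule, mostly by replacing the change score. These sizes rest on the assumed 0.8 SD effect, correlations of 0.3 to 0.7 and 5 to 20 tested variables, none of which the documents supply. The direction of the ANCOVA gain over the change score does not depend on the effect size: (1 + ρ)/2 is below 1 for any correlation under 1. The outcomes are tertiary or exploratory in a 40-patient pilot without a power calculation, so the consequence is for interpretation and for planning the next trial. Priority is modest.

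**What to change.** - Delete the baseline-significance group-assignment score from the Data Management paragraph, and the imbalance and univariate triggers from the tertiary-aims text.
- For each outcome, name one main analysis: ANCOVA of the 3-month value on randomised group plus the baseline value of that outcome.
- Keep the SAP's fixed covariate list, with an explicit group term, as a named sensitivity model.
- Report baseline balance descriptively, without tests.
- Treat the attrition score separately, for example as a missing-data sensitivity analysis, so that it is not dropped by accident with the other rule.

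The cost is wording in the protocol and SAP; no new data are needed. The SAP is written in the past tense, so the analyses may already have been run. In that case, state which rule was followed and report the baseline-adjusted group contrast, labelled as specified afterwards. The downside is that a chance imbalance in a variable outside the main model is handled only in the sensitivity analysis.
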